6 STUDY INTERVENTION

6.1 STUDY INTERVENTION ADMINISTRATION

6.1.1 STUDY INTERVENTION DESCRIPTION

This study will test a web-based application focused on healthy relationships and sexual assault. The web-based application will provide information and resources using a life-skills approach. Participants will also have the opportunity to set personal goals, find resources, and evaluate their interpersonal relationships and self-care. This web-based application will have the ability to be utilized on any smartphone, tablet, laptop, or desktop computer.

6.1.2 DOSING AND ADMINISTRATION

Intervention group participants will have six months to interact with the WebApp content, as this time period should present sufficient time for meaningful short-term change in the outcomes of interest. Further, the study will run for the duration of the school year, allowing study staff to follow students from the beginning of the school year to the end of the school year as they interact with the WebApp content. Study participants can choose to interact with the WebApp and take study surveys whenever is comfortable and safe for them to do so.

6.2 PREPARATION/HANDLING/STORAGE/ACCOUNTABILITY

6.2.1 ACQUISITION AND ACCOUNTABILITY

The web-based application was created through collaboration with students, stakeholders, and topical experts and developed by the Center for Health Communications Research (CHCR) through a modification of the pre-existing iCON platform. CHCR will maintain the WebApp servers throughout the entirety of the study.

6.2.2 FORMULATION, APPEARANCE, PACKAGING, AND LABELING

Not Applicable

6.2.3 PRODUCT STORAGE AND STABILITY

Not Applicable

6.2.4 PREPARATION

The web-based application was created through collaboration with students, stakeholders, and topical experts and developed by the Center for Health Communications Research (CHCR) through a modification of the pre-existing iCON platform.

6.3 MEASURES TO MINIMIZE BIAS: RANDOMIZATION AND BLINDING

Study subjects will be randomized into one of two groups: 1) Intervention (WebApp and current prevention programming on campus) or 2) Control (current prevention programming on campus only), with 150 students in each group. We will use cluster-randomization by residence hall (to minimize contamination associated with individual-level randomization of students living in the same residence hall).

This study will not involve blinding.

6.4 STUDY INTERVENTION COMPLIANCE

Not Applicable

6.5 CONCOMITANT THERAPY

Not Applicable

6.5.1 RESCUE MEDICINE

Not Applicable

7 STUDY INTERVENTION DISCONTINUATION AND PARTICIPANT DISCONTINUATION/WITHDRAWAL

7.1 DISCONTINUATION OF STUDY INTERVENTION

All participation is voluntary. There is no penalty to anyone who decides not to participate or who wishes to end participation during the study. All participants may choose not to answer a question at any point in the study.

If a participant discontinues use of the intervention during the research study, their data will be retained for attrition analyses.

7.2 PARTICIPANT DISCONTINUATION/WITHDRAWL FROM THE STUDY

All participation is voluntary. There is no penalty to anyone who decides not to participate or who wishes to end participation during the study. All participants may choose not to answer a question at any point in the study. All participants may choose to withdraw from the study at any time.

If a participant withdraws from the research study, their data will be retained for attrition analyses.

7.3 LOST TO FOLLOW-UP

If a participant withdraws from the research study or is lost to follow-up, their data will be retained for attrition analyses.

8 STUDY ASSESSMENTS AND PROCEDURES

8.1 EFFICACY ASSESSMENTS

The efficacy of this study is not a primary outcome as this is a pilot study focused on safety, acceptability, usability, and willingness to use. However, a number of measures will be used to gather preliminary data for future scale-up at all three time points (baseline, 3-months, and 6-months). Study participants' experiences with sexual violence (victimization and perpetration) will be assessed with 20 items from the Sexual Experiences Survey (SES) (Koss et al., 2007). Endorsement of rape myths will be measured with 22 items from the modified Illinois Rape Myth Acceptance Scale (McMahon & Farmer, 2011). The multidimensional nature of power in relationships will be measured by 6 items from the Sexual and Relationship Power Scale (SRPS) (Pulerwitz & Barker, 2000). All of these are measures have been validated and used extensively in the United States to measure knowledge and attitudes related to gender based violence. Additionally, knowledge about healthy relationships will be assessed with an investigator created 8-item scale.

8.2 SAFETY AND OTHER ASSESSMENTS

The safety of the WebApp will be assessed through post-intervention semi-structured interviews, conducted with 25 participants including 15 participants from the intervention group and 10 participants from the control group.

8.3 ADVERSE EVENTS AND SERIOUS ADVERSE EVENTS

8.3.1 DEFINITION OF ADVERSE EVENTS (AE)

Adverse event means any untoward medical occurrence associated with the use of an intervention in humans, whether or not considered intervention-related (21 CFR 312.32 (a)).

8.3.2 DEFINITION OF SERIOUS ADVERSE EVENTS (SAE)

An adverse event (AE) or suspected adverse reaction is considered "serious" if, in the view of either the investigator or sponsor, it results in any of the following outcomes: death, a life-threatening adverse event, inpatient hospitalization or prolongation of existing hospitalization, a persistent or significant incapacity or substantial disruption of the ability to conduct normal life functions, or a congenital anomaly/birth defect. Important medical events that may not result in death, be life-threatening, or require hospitalization may be considered serious when, based upon appropriate medical judgment, they may jeopardize the participant and may require medical or surgical intervention to prevent one of the outcomes listed in this definition.

8.3.3 CLASSIFICATION OF AN ADVERSE EVENT

8.3.3.1 SEVERITY OF EVENT

For adverse events (AEs) not included in the protocol defined grading system, the following guidelines will be used to describe severity.

- **Mild** – Events require minimal or no treatment and do not interfere with the participant's daily activities.
- **Moderate** – Events result in a low level of inconvenience or concern with the therapeutic measures. Moderate events may cause some interference with functioning.
- **Severe** – Events interrupt a participant's usual daily activity and may require systemic drug therapy or other treatment. Severe events are usually potentially life-threatening or incapacitating. Of note, the term "severe" does not necessarily equate to "serious".

8.3.3.2 RELATIONSHIP TO STUDY INTERVENTION

All adverse events (AEs) must have their relationship to study intervention assessed by the study staff. The degree of certainty about causality will be graded using the categories below. In a clinical trial, the study product must always be suspect.

- **Related** – The AE is known to occur with the study intervention, there is a reasonable possibility that the study intervention caused the AE, or there is a temporal relationship between the study intervention and event. Reasonable possibility means that there is evidence to suggest a causal relationship between the study intervention and the AE.
- **Not Related** – There is not a reasonable possibility that the administration of the study intervention caused the event, there is no temporal relationship between the study intervention and event onset, or an alternate etiology has been established.

8.3.3.3 EXPECTEDNESS

The Principle Investigator will be responsible for determining whether an adverse event (AE) is expected or unexpected. An AE will be considered unexpected if the nature, severity, or frequency of the event is not consistent with the risk information previously described for the study intervention.

8.3.4 TIME PERIOD AND FREQUENCY FOR EVENT ASSESSMENT AND FOLLOW-UP

The occurrence of an adverse event (AE) or serious adverse event (SAE) may come to the attention of study personnel during study visits and interviews of a study participant upon review by a study monitor.

All AEs including local and systemic reactions not meeting the criteria for SAEs will be captured on the appropriate case report form (CRF). Information to be collected includes event description, time of onset, clinician's assessment of severity, relationship to study product (assessed only by those with the training and authority to make a diagnosis), and time of

resolution/stabilization of the event. All AEs occurring while on study must be documented appropriately regardless of relationship. All AEs will be followed to adequate resolution.

Changes in the severity of an AE will be documented to allow an assessment of the duration of the event at each level of severity to be performed. AEs characterized as intermittent require documentation of onset and duration of each episode.

The Clinical Research Coordinator will record all reportable events with start dates occurring any time after informed consent is obtained until the last day of study participation. Events will be followed for outcome information until resolution or stabilization.

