1 PROTOCOL SUMMARY

1.1 SYNOPSIS

Participant Duration:	For pilot study – 9 months
Title:	MKit: A Pilot Study Testing a Life Skills Application to Address Interpersonal Relationships in College
Study Description:	This study utilizes implementation science principles to culturally adapt a pre-existing web-based application (WebApp) for use with college students. We will use the ADAPT-ITT process to adapt the WebApp to a diverse (race, ethnicity, gender/sexual identity) college population with a focus on life skills and holistic self-care as reinforcement to currently available primary prevention programming available to freshman students. Our hypothesis is that the adapted WebApp will be safe, acceptable, and students will be willing to use it as a reinforcement to current university primary prevention programming.
Objectives:	
• Primary: To evaluate the safety, usability, acceptability, and willingness of using the adapted WebApp among a randomized sample of 300 first year university students.• Secondary: To complete preliminary evaluations on efficacy measures such as sexual victimization/perpetration, rape myth acceptance, and power in sexual relationships to allow for power calculations for a future R-level submission.
Endpoints:	
• Primary: Safety (qualitative interviews), Usability (System Usability Scale, Brooke, 1986), Acceptability (investigator generated), and willingness to use (qualitative interviews).• Secondary: Sexual victimization/perpetration (Sexual Experiences Survey, Koss et al., 2007), Illinois Rape Myth Acceptance – Modified (McMahon & Farmer, 2011), Sexual Relationship Power Scale (Pulerwitz, Gortmaker, & DeJong, 2007)
Study Population:	300 first year university students (150 Control Group, 150 Intervention Group)
Phase:	Pilot
Description of Sites/Facilities Enrolling Participants:	University of Michigan Residence Halls (South and West Quad)
Description of Study Intervention:	Web-based app that uses a life skills approach to address healthy relationships and sexual violence.
Study Duration:	2 years 9 months

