At 3 and 6 months, we will repeat all baseline measures in both groups. Participants in the Intervention group will also be asked to complete the 10-item System Usability Scale (Brooke, 1996) and an investigator creates 5-item acceptability scale.

Post-intervention semi-structured interviews will be conducted with 25 participants including 15 participants from the intervention group and 10 participants from the control group to assess perceived safety, reaction to content, desirability, willingness to continue using the content, and willingness to recommend the content to others. Prior to commencing the interviews, we will ask each participant to complete a paper demographic survey.

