4.2 SCIENTIFIC RATIONALE FOR STUDY DESIGN

This is a before-and-after quasi-experimental, mixed-method pilot design with three survey collection points and a post-study semi-structured interview component. This study will be performed with healthy college students to determine the safety, acceptability, and usability of the WebApp.

The endpoints are common outcomes of interest for studies of technological interventions. These outcomes will be measured throughout the study, to observe changes over time with continued exposure to the intervention. These endpoints are important outcomes, as interventions must be safe, acceptable, and usable to ensure broad scale uptake. As the WebApp under study is a

primary sexual violence prevention intervention, experiences of sexual violence victimization and perpetration, as well as rape myth acceptance and relationship power (both upstream factors contributing to sexual violence perpetration) are outcomes of interest. Though this pilot study is not powered to detect changes in these secondary outcomes, obtaining data for power calculations for a larger study is a key component of this study.

This study compares usual care for the prevention of sexual violence with care as usual plus the intervention. Both groups will receive interventions currently in place, ensuring that standard care is not withheld from any participant. As the intervention under study is intended to supplement and reinforce current primary prevention programming, the study design will measure the acceptability and preliminary efficacy of broad scale-up of the intervention to the broader college campus.

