10.1.8 QUALITY ASSURANCE AND QUALITY CONTROL

The investigators will perform internal quality management of study conduct, data, documentation, and completion.

Any study problems with the WebApp, including any problems with the study WebApp and surveys, communicated through the study email address ([contact]) by study participants, will be addressed by the study team in a timely fashion.

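### Section 8.3.4 looks for adverse events at study visits that the schedule does not contain, so a low adverse event count could not be read as evidence of safety

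*Combined protocol and SAP*

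**What the plan says.** Section 8.3.4 describes how AEs become known: an event "may come to the attention of study personnel during study visits and interviews of a study participant upon review by a study monitor". The same section sets a full documentation duty: "All AEs occurring while on study must be documented appropriately regardless of relationship". Events are recorded from consent until the last day of participation, on a case report form, with onset, severity, relationship and resolution, and are followed until resolved or stable.

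Section 4.2 gives the design as "three survey collection points and a post-study semi-structured interview component". The schedule of activities (1.3) matches this. It has no visit and no AE row, and its one safety entry is perceived safety, at the interview. Consent and surveys in the pilot are online (5.5, 10.1.1.2), and section 6.1.2 adds: "Study participants can choose to interact with the WebApp and take study surveys whenever is comfortable and safe for them to do so".

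Under section 8.2, safety is assessed by interviews "conducted with 25 participants including 15 participants from the intervention group and 10 participants from the control group". Interviewees volunteer on the last page of the 6-month survey (5.5).

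Section 10.1.8 has the study team deal promptly with "Any study problems with the WebApp, including any problems with the study WebApp and surveys, communicated through the study email address". Section 10.1.3 states that survey and app-use data are not linked to any identifying information, and section 10.1.9.1 gives staff de-identified data.

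**The concern.** The detection rule and the schedule do not fit each other. One of the two named routes, the visit, does not exist. The other, the interview, reaches a small group once, after the 6-month survey. Yet the duty to document covers all participants for the whole study.

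This matters because safety is a primary objective (1.1, section 3), and section 9.4.1 expects the results to establish the safety of the app. Section 2.3.1 itself names emotional discomfort as a risk. The reporting rules in 8.3.5, 8.3.6 and 8.4.2 only start once somebody knows of an event. If few events are recorded, the reader cannot tell whether few occurred or few were asked about. The students most likely to be missed are those who stop early because of distress, since they never reach the page that carries the interview invitation.

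The point here is how AEs are found. How the interview data are analysed for safety is a separate matter.

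**Working it through.** **1. The plan's own figures.** From 1.1 and 8.2: 150 + 150 = 300 students; 15 + 10 = 25 interviewed.

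- Interviewed: 25/300 = 8.3%. Not interviewed: 275/300 = 91.7%.
- Intervention arm not interviewed: 135/150 = 90.0%.
- Control arm not interviewed: 140/150 = 93.3%.

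**2. Each contact set against the question of whether it asks about AEs.**

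- *Study visits (8.3.4):* none in 1.3, 4.1 or 4.2.
- *Post-study interview:* asks about perceived safety; 25 volunteers, once.
- *3- and 6-month surveys:* section 4.1 says "At 3 and 6 months, we will repeat all baseline measures in both groups", so they are addressed to all 300. The listed measures are demographics, knowledge, rape myth acceptance, sexual experiences and relationship power, plus usability and acceptability in the intervention arm. None is identified as AE capture. With unlinked answers, an event reported there could not be followed to resolution as 8.3.4 requires.
- *Study email (10.1.8):* described for app and survey problems, and unprompted.

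So 275 of 300 students are asked about AEs by no procedure that the documents designate for it.

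**3. What this could do to an AE count (illustration).** The documents give no AE rate and no expected response rate, so both are assumptions. Let *p* be the proportion of app students with an event of the kind of interest. The chance that at least one such event falls among *n* students who are asked is 1 − (1 − *p*)^*n*. Take *n* = 15 (app interviewees, treated as a random sample) and *n* = 0.70 × 150 = 105 (app students answering a survey question, with full disclosure).

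| Assumed *p* | Expected among 150 | *n* = 15 | *n* = 105 |
|---|---|---|---|
| 1% | 1.5 | 1 − 0.99^15 = 14% | 1 − 0.99^105 = 65% |
| 2% | 3 | 1 − 0.98^15 = 26% | 1 − 0.98^105 = 88% |
| 5% | 7.5 | 1 − 0.95^15 = 54% | 1 − 0.95^105 = 99.5% |

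At 2%, the interviews would contain no event about three times in four (1 − 0.26 = 0.74), although 3 are expected in the arm. Response is set at 70% because a comparison with all 150 students (1 − 0.98^150 = 95%) would flatter the survey.

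**The case against.** The strongest reply is that the plan has more routes than visits and interviews. Several parts of it stand.

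- Every student has scheduled surveys at 3 and 6 months. A reader might infer that nine in ten have no scheduled contact at which an AE could surface; that goes too far. The Sexual Experiences Survey records victimization at every wave (1.3, 8.1), which is a harm, although nothing routes it to AE reporting.
- Section 8.3.4 says that events may come to attention in the ways it names, so the list is not exclusive. A study email exists, and all participants receive resources for discomfort (2.3.1). A reader might infer that the AE log would be nearly empty whatever the app does, that a near-zero count would be an artefact, or that harm could not be found in time to act. The documents support none of these. A low count might be true; the plan gives no means of knowing.
- The wording of the 5-item acceptability scale is not given, and the consent forms are not in the text reviewed. One cannot say that no item touches on distress, or that students are not told how to report problems. What can be said is that no item is designated for AEs.
- The protocol rates the risk as no more than minimal (2.3.1), and how much active questioning such a pilot needs is partly judgement.
- The illustration is limited. Interviewees are volunteers chosen partly by user status (5.5), not a random sample. AEs as defined in 8.3.1 include unrelated events, whose rate could be well above those assumed.

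None of this supplies the missing piece: a procedure that asks the other 275 students.

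**Conclusion.** The point holds in limited form. Section 8.3.4 relies on visits that are not in the schedule, and outside 25 interviews no designated procedure asks about AEs, while every AE is to be documented. This affects 275 of 300 students (92%) and 135 of 150 app students (90%); these figures rest only on the planned numbers. The consequence is that a low AE count would be uninformative and could not be read as evidence of safety.

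The detection chances (14%, 26% and 54% among 15, against 65%, 88% and 99.5% among 105) show the scale only. They depend on the assumed AE rates, 70% response, full disclosure and random selection of interviewees. If students with distress leave early, the interviews would do worse than shown; the survey figures would also fall if such students do not respond.

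Given the stated minimal risk, this is a change that should be made, not one on which the whole trial depends. It is worth making because safety is a primary objective and two survey waves already exist to carry the question.

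**What to change.** 1. In 8.3.4, replace the reference to study visits with the contacts that exist: the 3- and 6-month surveys, the interviews and the study email.
2. Add one AE question with free text to both follow-up surveys in both arms. It should ask about any health problem or distress since the last survey, whether or not the student links it to the study, because 8.3.4 covers unrelated events too. Mention the app only in the intervention version.
3. Add a separate opt-in form by which a student can ask to be contacted, kept apart from the survey answers.
4. Reconcile the follow-up requirement in 8.3.4 with the unlinked data described in 10.1.3 and 10.1.9.1, stating what can and cannot be followed up.
5. Report AE counts by arm beside the numbers asked and answering, and do not present a low count as evidence of safety without them.

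The cost is one extra item at two existing waves and an IRB amendment. The limits should be stated: events are self-reported and may be up to three months old when reported, and follow-up is possible only for students who opt in.

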8.3.5 ADVERSE EVENT REPORTING

The Primary Investigator will immediately report to the sponsor any adverse event, whether or not considered study intervention related, including breach of confidentiality or lack of safety whether there is a reasonable possibility that the study intervention caused the event. All adverse events (AEs) will be followed until satisfactory resolution or until the site investigator deems the event to be chronic or the participant is stable. Other supporting documentation of the event may be requested by the study sponsor and should be provided as soon as possible.

8.3.6 SERIOUS ADVERSE EVENT REPORTING

The Primary Investigator will immediately report to the sponsor any serious adverse event including lack of safety whether there is a reasonable possibility that the study intervention caused the event. All serious adverse events (SAEs) will be followed until satisfactory resolution or until the site investigator deems the event to be chronic or the participant is stable. Other supporting documentation of the event may be requested by the study sponsor and should be provided as soon as possible.

